Oral glucose tolerance tests with glucose (G) and insulin (I) measured at 0, 30, 60, and 120 after glucose load to assess diabetes, insulin resistance and pancreatic β -cell function will be performed 32 (+4) weeks after study medications are started. Testing will be repeated at 56 (+4) weeks and 80 (+4) weeks after treatment start. The baseline blood samples from the OGTT will also be analyzed for liver enzymes, TSH, creatinine with eGFR (baseline and 56 weeks only), and lipid profile. Subjects will remain on treatment unless they are diagnosed with DM2 during an OGTT or a random blood test at which time final testing will be performed. They will be withdrawn from the study and they will be referred to a specialist for additional treatment of

diabetes. In subjects who complete 80 (+4) weeks of treatment, all study medications will be stopped and subjects will be asked to return for routine OGTT testing by their physician.

Primary Study Endpoint:

- An index of *insulin secretion in relation to insulin resistance (IS-SI)* will be calculated. Thus, β -cell compensatory capacity will be evaluated by the insulin sensitivity-secretion index (IS-SI) defined as the product of composite insulin sensitivity index and first-phase insulin release index (insulinogenic index).

Secondary Study Endpoint(s):

- Indexes of insulin sensitivity and secretion using the serum glucose and insulin concentrations obtained in the fasting state and during the 2hr OGTT with INS will be computed by several measures previously validated in women. Changes in insulin resistance –baseline {HOMA-IR} and composite insulin sensitivity index [ISI_{OGTT}], and pancreatic β -cell function (corrected insulin response [CIR_{glupeak}] and insulinogenic index [IGI])/HOMA-IR
- Anthropometric measurements [BMI, absolute body weight, waist circumference, waist: hip ratio,
- Cardiometabolic risk measures [lipids, liver enzymes; blood pressure]
- Development of diabetes, impaired glucose tolerance or impaired fasting glucose based on positive OGTT. Glucose tolerance will be defined as normal, impaired glucose tolerance (IGT) or diabetic according to the criteria of the American Diabetes Association.¹ Patients diagnosed with diabetes will be withdrawn from the study and referred to a specialized physician.

Biochemical assays and calculations

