The primary outcome measure is the insulin sensitivity-secretion index (IS-SI) and secondary outcome measures include changes in lipid and hepatic enzyme levels, anthropometric parameters, insulin sensitivity and pancreatic β -cell function, and glucose tolerance status. Continuous variables will be tested for normality of distribution using the Kolmogorov-Smirnov test. Natural log transformations of skewed variables will be used where necessary in subsequent analyses. For variables with highly skewed distributions, a logarithmic transformation will be done first and the geometric means reported instead. Differences in effects of drug intervention for continuous variables (in their raw or transformed state) will be compared using Subjects/Drug Treatments by trials analyses of variance (ANOVAs). This analysis provides p values for differences between groups/drug treatments (A), differences over time (B), and the interaction of group/drug treatment with time (AB). Otherwise, changes between baseline and follow-up measurements will be compared between groups by Wilcoxon's nonparametric methods. Anthropometric measurements (body weight, BMI), blood pressure, direct and indirect measurements of carbohydrate metabolism (HOMA, SI_{OGTT} , CIRgp, IGI, and ISSI), and measurements of lipid profile (total cholesterol, HDL, LDL), and liver enzymes (ALT, AST) will be considered as dependent variables. The simultaneous effect of various baseline characteristics and characteristics at certain study treatment intervals between women who did not develop diabetes and women who did during follow-up will be studied with the use of a linear multiple regression analysis. Diabetes and IGT occurrence before and after different treatment will be compared with the McNemar test (complex chi square for paired data), which formally tests for a change between the observed proportions of 2 related samples.

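### Predictors of developing diabetes are to be studied by linear regression, although the outcome is, on the natural reading, yes/no and women leave the study at diagnosis

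*Combined protocol and SAP*

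**What the plan says.** The Statistical Analysis Plan sets out one analysis of which women progress: "women who did not develop diabetes and women who did during follow-up will be studied with the use of a linear multiple regression analysis". The explanatory side of that model is described only as "various baseline characteristics and characteristics at certain study treatment intervals". The plan does not name the dependent variable, list the characteristics or say which intervals are meant.

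Development of diabetes is a secondary endpoint, classified by OGTT: "Glucose tolerance will be defined as normal, impaired glucose tolerance (IGT) or diabetic according to the criteria of the American Diabetes Association". Under Randomization and Allocation, the first on-treatment OGTT "will be performed 32 (+4) weeks after study medications are started", and "Testing will be repeated at 56 (+4) weeks and 80 (+4) weeks after treatment start". Subjects stay on treatment "unless they are diagnosed with DM2 during an OGTT or a random blood test at which time final testing will be performed". Then: "They will be withdrawn from the study and they will be referred to a specialist".

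On missing values, the Statistical Analysis Plan says only that all available data for the relevant follow-up period will be used. It gives no rule for values that do not exist because a woman has been withdrawn. The one other analysis of diabetes occurrence is a McNemar before/after comparison, which does not examine predictors.

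**The concern.** Three things come together in that sentence.

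- **Model type.** If the outcome is whether a woman developed diabetes, its variance depends on the risk itself, so the constant-variance standard errors of linear regression are wrong. Fitted risks can fall below zero. A woman followed for 32 weeks without diabetes counts the same as one followed for 84 weeks.
- **Later-visit regressors.** A woman diagnosed at week 32 has no week-56 or week-80 value. Ordinary regression needs a complete row for each woman. Unless a rule supplies the missing values, a model with a later-visit regressor is fitted mainly to late cases.
- **Values at the diagnosing visit.** If the final test at diagnosis stands in for the missing visit, the glucose- and insulin-based indices come from the OGTT that may itself have made the diagnosis. Part of the association is then built in.

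Preventing or delaying type 2 diabetes is the stated rationale of the trial. The result at stake is its account of who progresses and why.

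**Working it through.** **Inputs**

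- Enrolment of 150, a total of 118 for power, dropout 20–22%, follow-up 32–84 weeks: Sample Size Computation and Power Analysis.
- OGTTs at weeks 32, 56 and 80, with withdrawal at diagnosis: Randomization and Allocation.
- Diabetes incidence of 4.6% per year (pioglitazone) and 13.1% per year (placebo) in Hispanic women with prior GDM: Study Background and Rationale. The plan gives no rate for this trial, so these serve only as an assumed range.

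**The plan's own figure.** No number is attached to the regression. The enrolment target, which supplies the denominator, reproduces: 118/(1 − 0.20) = 147.5, 118/(1 − 0.21) = 149.4 and 118/(1 − 0.22) = 151.3, so 150 is consistent with the stated dropout.

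**Expected cases by visit.** Take the annual rate r as a constant hazard, with detection only at visits and no dropout. The proportion still free of diabetes at week w is S(w) = exp(−r·w/52).

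| | r = 0.046 | r = 0.131 |
|---|---|---|
| S(32), S(56), S(80) | 0.9721, 0.9517, 0.9317 | 0.9225, 0.8684, 0.8175 |
| Cases at week 32: 150·[1 − S(32)] | 4.2 | 11.6 |
| Cases at week 56: 150·[S(32) − S(56)] | 3.1 | 8.1 |
| Cases at week 80: 150·[S(56) − S(80)] | 3.0 | 7.6 |
| Total by week 80: 150·[1 − S(80)] | 10.2 | 27.4 |
| Share found by week 32 | 40.9% | 42.4% |
| Share found by week 56 | 70.7% | 72.1% |

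If the rate is read instead as an annual proportion, S(w) = (1 − r)^(w/52). The totals become 10.5 and 29.1, and the shares 40.9–42.6% and 70.8–72.2%.

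**Loss in a complete-case model.** A week-56 regressor excludes the women diagnosed at week 32, about 41–43% of cases. A week-80 regressor excludes those diagnosed at weeks 32 and 56, about 71–72%, and leaves about 3 to 8 cases.

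**Effect of dropout on the counts.** Scaled to 118 women, the totals are 10.2 × 118/150 = 8.0 and 27.4 × 118/150 = 21.6.

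**Linear fit to a yes/no outcome.** The variance at risk p is p(1 − p). At the two week-80 risks above it is 0.068 × 0.932 = 0.063 and 0.183 × 0.817 = 0.150, a ratio of about 2.4. In 1,000 simulated datasets of 150 women per scenario, with two standard-normal regressors and assumed log-odds ratios of 0.7 or 1.1 each, the mean share of women with a fitted risk below zero was:

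- 13–20% at a cumulative incidence of 7%;
- 8–15% at a cumulative incidence of 19%.

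The effect sizes are illustrative and do not come from the plan.

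**The case against.** The strongest objection is that the dependent variable is an inference. The preceding sentence of the Statistical Analysis Plan lists continuous measures (weight, blood pressure, HOMA, ISSI, lipids, enzymes) as dependent variables. Diabetes status could then be the grouping factor, and linear regression would be the right type. This cannot be excluded. It is strained, because the sentence speaks of the simultaneous effect of the characteristics, which makes them the explanatory side. Even so, the missing later values and the shared OGTT would remain, and the outcome would still need naming.

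A reader might also infer that the plan discards women diagnosed early. It does not say so. No case-wise deletion is prescribed, all available data are to be used, and final testing is required at diagnosis. A model with only baseline and week-32 values keeps the week-32 cases, though their glucose-based week-32 values may then come from the diagnosing test. The 41–43% and 71–72% are what follows if week-56 or week-80 regressors enter a complete-case fit.

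The visit split is idealised. A random blood test can also give the diagnosis, dropout is expected, and the rates come from another population and treatment, whereas every woman here takes metformin.

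Nor is every on-treatment value circular. Weight, BMI, blood pressure, lipids and liver enzymes do not define diabetes. The problem is confined to glucose- or insulin-derived values from the diagnosing OGTT.

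Finally, this is a supporting analysis in a self-described pilot whose primary endpoint and sample size rest on IS-SI. That objection stands, and it limits the severity.

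**Conclusion.** The concern holds as a should-fix. On the natural reading, the plan applies linear regression to a yes/no outcome with unequal follow-up, and that model is unsuitable whatever the diabetes rate. The case losses are conditional on complete-case fitting, later-visit regressors, a constant rate of 4.6–13.1% per year, detection only at visits and no dropout. The expected 10–27 cases rest on the same rates, visit schedule and no-dropout assumption. The broad conclusion, that there are too few cases for many characteristics at several intervals, would be stronger with fewer cases.

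The documents do not support saying that the plan mandates dropping early cases, that all on-treatment associations are circular, or that the trial's main result is compromised. The primary IS-SI comparison does not depend on this regression.

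**What to change.** Replace the regression sentence in the Statistical Analysis Plan with wording that does the following.

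1. Names development of diabetes as the outcome, and says how a diagnosis by random blood test between visits is assigned to an interval.
2. Uses a discrete-time (complementary log-log) or similar time-to-diagnosis model, so that each woman contributes only the intervals in which she was at risk.
3. Includes treatment and at most one or two prespecified baseline covariates, with penalised likelihood if cases are few. A rule of thumb of ten cases per term would allow about one term at 10 cases and two at 27. Treatment plus one covariate is therefore already tight at the low end, and a second needs justification.
4. Allows on-treatment values only if measured at a visit before diagnosis, among women still at risk.
5. Labels the analysis exploratory.

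The cost is a change of wording, with no new visits or data. The team should confirm that SPSS 15.0, the package named in the plan, fits the chosen model, or name another. The real downside is that fewer characteristics can be examined, which the expected number of cases requires in any event.

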Subjects will be equally randomized to one of two treatment groups: Metformin + Liraglutide or Metformin + Placebo. All patients will be taking either liraglutide 6 mg/ml or

placebo solution for injection in a 3 ml pre-filled pen which is self-administered via subcutaneous injection once per day in the abdomen or thigh. For patients taking liraglutide, treatment will be initiated at 0.6 mg subcutaneous, increased to 1.2 mg and then to 1.8 mg subcutaneous, as tolerated, during the 4-wk non-forced dose-escalation period up to a maximum allowed dose of 1.8 mg subcutaneous daily. Placebo-treated subjects will undergo the same non-forced dose-escalation regimen, using matching injections. All patients will be receiving therapy with metformin which will be started at an initial dose of metformin of 500 mg daily (with dinner) for 2 weeks. They then will be increased to a metformin dose of 500 mg BID (breakfast and dinner). The dose will be increased to 500 mg am, 1000 mg pm (with breakfast and dinner) for 2 weeks and then increased to the final dose of 1000 mg BID (breakfast and dinner) until the end of the study. For patients who cannot tolerate the full dose of metformin in combination with liraglutide, the metformin dose will be adjusted at the discretion of the physician to a level that is tolerable. The physician investigator or research nurse will dispense a ten-week supply of the appropriate study medication to the subject at the time of randomization and every ten weeks thereafter. All patients will have a urine pregnancy test performed to document they are not pregnant prior to receiving the next 10 weeks of medication. Appointments will be made to return every ten weeks to receive a new supply of medication. All patients will receive the same counseling concerning the benefits of lifestyle modification through diet and exercise. Patients in each group will receive standardized dietary advice and appropriate written information on a balanced weight-reducing diet. The patients will be also encouraged to increase daily exercise (such as walking, using stairs), although this will not be formally assessed. The participants will receive further encouragement to adhere to the regime at their 32 (+4) week, 56 (+4) week and 80 (+4) week review visits and during follow-up phone calls.

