All analyses will be conducted with subjects assigned to their initial treatment group, using all available data for the period of follow-up relevant to the particular analysis. Data will be analyzed on the basis of intention to treat and also on completed treatment parameters where relevant. Differences of $P < 0.05$ will be considered statistically significant. Results will be reported as mean \pm standard error of the mean (S.E.M) for quantitative variables and percentages for categorical variables unless otherwise noted. We will perform all statistical analyses using SPSS 15.0 for Windows (SPSS, Inc.; Chicago, Ill).

Study Drugs

Description

Both active drug (Liraglutide 6.0 mg/ml injection) and placebo will be supplied by Novo Nordisk A/S. as a pre-filled pen for subcutaneous injection. Each liraglutide pre-filled pen contains 18 mg/3 ml (6 mg/ml) and will deliver 30 doses of 0.6 mg; 15 doses of 1.2 mg or 10 doses of 1.8 mg; the placebo pen will deliver equal volumes of vehicle solution only. Liraglutide and placebo are visually identical.

Metformin Hydrochloride XR (extended-release) in 500 mg strength oral tablets will be purchased in bulk through the Woman's Hospital Infusion Pharmacy. Metformin hydrochloride XR is combined with a drug release controlling polymer so that drug is released slowly from the dosage form. The medication will be allocated into appropriate patient dosage regimens by the hospital pharmacy personnel. Dosage of metformin XR will be prescribed according to standard directions and not exceeding the maximum recommended daily dose in adults of 2000 mg.

Trial Supplies

Double-blind Liraglutide or placebo

Liraglutide 6.0 mg/ml or placebo solution for injection in a 3 mL pre-filled pen will be supplied by Novo Nordisk A/S. The pre-filled pen will be provided as a pen-injector. The Investigator will provide each subject with Direction for Use for the liraglutide pen-injector at each dispensing visit.

Packaging and Labelling of Trial Products

Liraglutide and placebo will be packed and labelled by Novo Nordisk A/S and provided in non subject specific boxes. Labelling will be in accordance with Annex 13, local law and trial requirements.

Storage, Handling, Accountability and Destruction of Trial Products

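### Development of diabetes, IGT or IFG is a secondary endpoint, but the only test assigned to it is a before/after McNemar test, so no between-arm test or interval is planned

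*Combined protocol and SAP*

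**What the plan says.** Randomization and Allocation sets up two independent arms: "Subjects will be equally randomized to one of two treatment groups: Metformin + Liraglutide or Metformin + Placebo". The last item under Secondary Study Endpoint(s) is "Development of diabetes, impaired glucose tolerance or impaired fasting glucose based on positive OGTT". The same item then defines glucose tolerance in three categories (normal, IGT, diabetic), with no IFG category.

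For this outcome the Statistical Analysis Plan says "Diabetes and IGT occurrence before and after different treatment will be compared with the McNemar test", and describes the test as one "which formally tests for a change between the observed proportions of 2 related samples". IFG is not mentioned there.

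The other analyses in that section are:

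- ANOVA: "Differences in effects of drug intervention for continuous variables (in their raw or transformed state) will be compared using" a group-by-time analysis of variance.
- Wilcoxon: "Otherwise, changes between baseline and follow-up measurements will be compared between groups by" a nonparametric method. This sentence follows directly on the ANOVA description.
- A linear multiple regression contrasting women who did and did not develop diabetes. It names no treatment term.
- General rules: "All analyses will be conducted with subjects assigned to their initial treatment group", and results given as "percentages for categorical variables unless otherwise noted".

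**The concern.** The trial exists to compare combination therapy with metformin alone. A paired before/after test answers a different question: whether the proportion with diabetes or IGT changed over time. Run in each arm, it gives two p values and no contrast between them. Run on both arms together, it ignores treatment altogether.

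Separate within-arm p values also invite a known error, in which significance in one arm and not the other is read as a treatment effect. The two p values can fall on opposite sides of 0.05 when the arms hardly differ. The between-arm result would be two percentages that a reader cannot weigh, for the endpoint closest to the trial's rationale of preventing diabetes.

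**Working it through.** **Is there a between-arm method elsewhere?** The ANOVA is restricted to continuous variables. The Wilcoxon sentence is most naturally the fallback for those same variables, and diabetes and IGT then get their own sentence and their own test. The regression has no treatment term. Analysis by assigned group fixes the population, and percentages fix the display; neither is a test or an interval. IFG appears in the endpoint and in neither the three-category definition nor the McNemar sentence.

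**What McNemar does for diabetes alone.** The plan states no event rate or power for this endpoint, so there is no planned figure to reproduce. Inputs from the documents: 75 per arm and an average of 60 weeks of treatment (Sample Size Computation and Power Analysis), threshold 0.05 (taken as two-sided), and zero baseline diabetes (Major Exclusion Criteria). With no baseline cases, the test in one arm depends only on the number of conversions, k:

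- exact p = 2 × 0.5^k
- uncorrected chi-square = k on 1 df
- continuity-corrected chi-square = (k − 1)²/k on 1 df

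| k | Exact | Corrected | Uncorrected |
|---|---|---|---|
| 3 | 0.25 | 0.248 | 0.083 |
| 4 | 0.125 | 0.134 | 0.046 |
| 5 | 0.0625 | 0.074 | 0.025 |
| 6 | 0.031 | 0.041 | 0.014 |

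So an arm becomes significant at 6 conversions (exact or corrected) or at 4 (uncorrected). The plan does not say which form is meant.

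**Two examples** (Newcombe intervals, Fisher between arms):

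- 6/75 against 5/75: exact McNemar p = 0.031 and 0.0625. Between arms, the difference is 8.0% − 6.7% = 1.3 points (95% CI −7.7 to 10.5), Fisher p = 1.00.
- 4/75 against 3/75: uncorrected McNemar p = 0.046 and 0.083. Between arms, 5.3% − 4.0% = 1.3 points (−6.5 to 9.4), Fisher p = 1.00.

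**How often would exactly one arm be significant if the arms had the same risk?** This is illustration only. The annual rates are assumed: 4.6% and 5.4% are the pioglitazone and troglitazone arms cited in the background, and 9.04% = 13.1% × (1 − 0.31) combines one cited study's placebo rate with another population's metformin effect. Cumulative risk = 1 − exp(−rate × weeks/52.18). With q = P(Binomial(75, risk) ≥ 6), or ≥ 4 for the uncorrected test, the probability that exactly one arm is significant is 2q(1 − q).

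| Weeks | Rate/yr | Risk | One arm only, exact or corrected | One arm only, uncorrected |
|---|---|---|---|---|
| 60 | 4.6% | 5.15% | 31% | 50% |
| 60 | 5.4% | 6.02% | 42% | 44% |
| 60 | 9.04% | 9.87% | 36% | 10% |
| 80 | 4.6% | 6.81% | 48% | 37% |
| 80 | 5.4% | 7.95% | 49% | 25% |
| 80 | 9.04% | 12.94% | 12% | 2% |

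Under the same 60-week assumptions, a Fisher test between arms is falsely significant in 1.5%, 1.8% and 2.7% of trials (full enumeration).

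This arithmetic does not carry over to IGT, where women can move in both directions. McNemar for IGT is still a before/after test.

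**The case against.** The strongest reply is that the Wilcoxon sentence might cover this endpoint. The section opens by listing glucose tolerance status among the secondary outcomes whose changes are of interest; normal, IGT and diabetic are ordered; and a rank test on change would compare the groups. The list of dependent variables omits glucose tolerance status, but it also omits waist circumference and waist-to-hip ratio, so omission alone proves little. That last point stands, and the list should not carry the argument. The reading still fails on the structure of the text: the sentence completes the continuous-variable ANOVA, and diabetes and IGT are then given a different test by name. Even if accepted, it would give no interval and, on the three-category definition, nothing for IFG.

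Second, the figures assume diabetes tested alone, McNemar run per arm, and 75 evaluable women per arm despite an expected 20–22% dropout. If diabetes and IGT are pooled, the baseline count is not zero and the thresholds above do not apply. The one-arm-only frequency runs from 2% to 50%. It shows that the error can easily arise, not how large it will be. Nor does the plan say that significance in one arm would be read as a treatment effect.

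Third, this is a pilot, the endpoint is not among the stated objectives, and a between-arm test would have little power. That limits the severity. It does not justify leaving out the comparison: a pilot meant to inform later trials needs the between-arm estimate and its uncertainty.

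**Conclusion.** The concern holds. The plan assigns a paired test to an endpoint that calls for a comparison of independent randomised arms, and assigns nothing to IFG. This conclusion rests on the text and on no assumed rate. The clearest measure of its effect is 6/75 against 5/75: within-arm p values of 0.031 and 0.0625 for a difference of 1.3 points whose interval runs from −7.7 to 10.5. The frequencies under equal risk are illustrative and depend on the assumptions given with them. The primary IS-SI analysis is unaffected, so this should be fixed but does not threaten the trial's main result.

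**What to change.** Make the analysis of this endpoint a comparison of the randomised arms:

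1. **Diabetes.** Report incidence by arm with the risk difference and 95% CI. This alone closes most of the gap. Because status is assessed at 32, 56 and 80 weeks, add a discrete-time or log-rank comparison. State whether diabetes found on a random blood test counts: Study Design withdraws women on either basis, while the endpoint is defined by OGTT.
2. **Any abnormal glucose tolerance** (IFG, IGT, both, or diabetes) against normal at the last available OGTT. Use logistic regression on arm, adjusted for baseline status (normal or abnormal), with odds ratio and 95% CI. Count women withdrawn for diabetes as abnormal. Report by arm how many have no post-baseline OGTT and which visit supplied the last one.
3. **IFG.** Name it in the Statistical Analysis Plan and reconcile the two statements under Secondary Study Endpoint(s).
4. **McNemar.** Keep it only as within-arm description.

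The cost is wording in the Statistical Analysis Plan and one sentence of the endpoint definition; no new visits or data. The plan should say that this is estimation. At 75 per arm and under the assumed rates, power to detect a halved diabetes rate is about 4–12% (Fisher) or 11–21% (uncorrected chi-square) at 60 weeks, and 7–17% or 15–25% at 80 weeks. Even at the drug-versus-placebo contrasts cited in the background (12.1 against 5.4% and 13.1 against 4.6% per year), which are not add-on-to-metformin effects, power over 60–80 weeks is 22–48% (Fisher) or 31–57% (chi-square).

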Project Title: Effects of intervention with the GLP-1 analog liraglutide plus metformin versus metformin monotherapy in overweight/obese women with metabolic defects and recent history of gestational diabetes mellitus (GDM)

Principal Investigators: [name], M.Sc., PhD
[name].

Address Woman's Metabolic Health Center
Woman's Health Research Department
[name]
[name]

Clinical Trials registration number- NCT01234649

Effects of intervention with the GLP-1 analog liraglutide plus metformin versus metformin monotherapy in overweight/obese women with metabolic defects and recent history of gestational diabetes mellitus (GDM)

Project Overview/Summary

The objective of the present proposal is to compare the clinical, endocrine and metabolic effects of therapy with combination liraglutide and metformin to metformin monotherapy in overweight women with a recent history of GDM. This study will serve as a pilot investigation to open perspectives for future investigations combining insulin-sensitizing drugs with different mechanisms of action in former GDM women especially overweight women for whom standard treatment with metformin is less effective

Primary Objective:

- To determine if the addition of liraglutide to metformin therapy is more effective than monotherapy with metformin in improving pancreatic beta cell compensation (β -cell glucose sensitivity and rate sensitivity) in overweight/obese women with prior GDM who are at high risk of developing Type 2 diabetes (DM2).

Secondary Objective(s)

- To determine if the addition of liraglutide to metformin therapy is more effective than monotherapy with metformin in improving insulin sensitivity in overweight/obese women with prior GDM who are at high risk of developing Type 2 diabetes (DM2).
- To determine the impact of liraglutide in combination with metformin compared to metformin monotherapy on anthropometric measures in overweight/obese women with prior GDM who are at risk of developing DM2.
- To determine if the addition of liraglutide to metformin therapy is more effective than metformin alone in improving cardiometabolic markers (lipid profile and blood pressure) in overweight/obese women with prior GDM who are at risk of developing DM2.

Study Background and Rationale

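### One P < 0.05 rule covers every secondary outcome with no order, adjustment or exploratory label: with 13 outcomes, about a 12–28% chance of a false significant benefit (24–49% in either direction)

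*Combined protocol and SAP*

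**What the plan says.** The Statistical Analysis Plan sets one threshold for everything: any difference with P below 0.05 "will be considered statistically significant". It names one primary: "The primary outcome measure is the insulin sensitivity-secretion index (IS-SI").

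The same section then lists the dependent variables. The list opens with "Anthropometric measurements (body weight, BMI), blood pressure, direct and indirect measurements of carbohydrate metabolism"; the indices meant are HOMA, SI_OGTT, CIRgp, IGI and ISSI. The list closes with "measurements of lipid profile (total cholesterol, HDL, LDL), and liver enzymes (ALT, AST) will be considered as dependent variables". For each variable, the groups-by-trials ANOVA yields three p values: one for treatment group (A), one for time (B) and one for their interaction (AB). Results are to be produced by intention to treat and, where relevant, also for completed treatment.

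The Secondary Study Endpoint(s) section adds waist circumference, waist:hip ratio, IGI/HOMA-IR and glucose tolerance status. Study Design and Laboratory Measures include triglycerides in the lipid profile.

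Under Secondary Objective(s), the insulin-sensitivity and cardiometabolic objectives are comparative claims. The latter asks whether the combination is "more effective than metformin alone in improving cardiometabolic markers (lipid profile and blood pressure"). The anthropometric objective asks only about impact.

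No section gives a multiplicity adjustment, a testing order, a named key secondary outcome, or a statement that the secondary outcomes are exploratory.

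**The concern.** The rule treats a difference in AST exactly as it treats a difference in IS-SI. Two secondary objectives are worded as claims of superiority over a group of markers, and nothing says which marker decides the answer or whether the claim depends on the primary result. If IS-SI showed no difference, the plan as written would still allow a single lipid fraction or blood pressure reading below 0.05 to be reported as a significant benefit of adding liraglutide. With this many outcomes, such a result is fairly likely by chance alone. What is at stake is how far a reader can trust the secondary conclusions; the primary test is a separate matter.

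**Working it through.** The plan states no error rate for the secondary outcomes, so there is no figure of its own to reproduce.

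**Step 1. Count the between-arm secondary outcomes (IS-SI left out).**

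| Group | Variables | Count |
|---|---|---|
| Anthropometry | body weight, BMI | 2 |
| Blood pressure | named once; 2 if systolic and diastolic are separate | 1 (2) |
| Carbohydrate indices | HOMA, SI_OGTT, CIRgp, IGI | 4 |
| Lipids | total cholesterol, HDL, LDL | 3 |
| Liver enzymes | ALT, AST | 2 |
| **Named in the Statistical Analysis Plan** | | **12 (13)** |
| Added elsewhere | waist, waist:hip ratio, IGI/HOMA-IR, triglycerides | 4 |
| **Total** | | **16 (17)** |

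Glucose tolerance status is left out because the McNemar test described for it compares before with after, not arm with arm. The calculation uses m = 13, which is below the full count.

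**Step 2. Independent outcomes.** Sidedness is not stated. An ANOVA F test has no direction, so I assume one two-sided test per outcome at 0.05, of which 0.025 falls on the favourable side.

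- Any significant difference: 1 − 0.95^13 = 1 − 0.513 = 48.7%.
- A significant benefit: 1 − 0.975^13 = 1 − 0.719 = 28.1%.

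**Step 3. Correlated outcomes.** The documents give no correlations, so a range is shown. With common correlation ρ between the test statistics (each oriented so that positive is favourable) and c = 1.96:

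P(any) = 1 − ∫ [Φ((c − √ρ·t)/√(1−ρ)) − Φ((−c − √ρ·t)/√(1−ρ))]^13 φ(t) dt

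For a benefit, the second Φ term is dropped. Numerical integration gives:

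| ρ | Any direction | Benefit |
|---|---|---|
| 0 | 48.7% | 28.1% |
| 0.3 | 41.8% | 21.4% |
| 0.5 | 33.4% | 16.7% |
| 0.7 | 24.1% | 12.0% |

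**Step 4. Less uniform correlation.** A simulation of 400,000 draws put the 13 outcomes in five groups (2 anthropometric, 2 pressures, 4 carbohydrate, 3 lipid, 2 enzymes). Correlation was 0.5–0.8 within groups and 0–0.3 between them. The results were 34–44% in either direction and 17–25% for a benefit.

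**Step 5. Full count.** With 16 outcomes the independent values are 1 − 0.95^16 = 56.0% and 1 − 0.975^16 = 33.3%. At ρ = 0.7 they are about 26% and 13%.

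**Step 6. What is not counted.** Each ANOVA yields a group p value (A) and an interaction p value (AB), and the plan does not say which one decides. There may also be two analysis sets. Using both p values or both sets would raise these figures.

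**The case against.** The strongest reply is that this is a self-described pilot with one named primary outcome, which also drives the sample size. The other outcomes are labelled secondary. Leaving such outcomes unadjusted and reading them as supportive is common, and it does not inflate the primary test. All of that stands, and it makes the point less serious. It does not close the gap, because the plan never says that the secondary outcomes are supportive, and it calls them significant by the same rule as the primary.

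Several stronger readings are tempting and are not supported:

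- A reader might take 24–49% as the chance of a false benefit. It counts differences in either direction; the benefit figure is about half of that or slightly more.
- A reader might treat the top of the range as realistic. Independence conflicts with the documents' own definitions: BMI is computed from weight, LDL comes from the Friedewald equation, and HOMA-IR and ISI_OGTT share fasting glucose and insulin. Equally, a correlation of 0.7 for every pair is demanding, so neither end is likely.
- A reader might add separate tests at each of the three follow-up visits. The stated main method is one ANOVA across visits.
- A reader might say that all three secondary objectives are superiority claims over all these markers. Only two are. Liver enzymes appear in no objective, and CIR and IGI belong with the primary beta-cell question. The markers under the two comparative objectives number about 6 to 8, which gives 1 − 0.975^6 = 14% to 1 − 0.975^8 = 18% for a false benefit if they are independent.

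That one marker could carry a claim is an inference from the plan's silence. No section says so, but none prevents it.

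**Conclusion.** The gap is real and moderate in weight. For 13 secondary outcomes with one two-sided between-arm test each, the chance under no effect of at least one significant difference is about 24–49%, and of at least one significant benefit about 12–28%. The benefit figure compares with 2.5% for a single favourable two-sided test, so it is roughly 5 to 11 times as large (12.0/2.5 = 4.8; 28.1/2.5 = 11.2). These ranges rest on assumed correlations of 0.7 down to 0, on two-sided testing, and on a count of 13 that needs blood pressure split or one item added from another section. A reader might infer that the primary IS-SI result is compromised or that a formal testing hierarchy is required. The documents support neither: the primary error rate is untouched, and in a pilot an exploratory label is enough.

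**What to change.** In the Statistical Analysis Plan, replace the general significance sentence with one that reserves P < 0.05, and the terms significant and more effective, for the primary between-arm IS-SI comparison. The sentence should also say which ANOVA p value is that comparison. State that all secondary outcomes will be reported as between-arm estimates with 95% confidence intervals and nominal P values, labelled supportive or exploratory.

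Optionally, if the sponsor wants confirmatory secondary claims, it may name in advance one measure for each of the three secondary objectives. These would be tested only after a significant primary result, with Holm adjustment (0.05/3 = 0.0167, then 0.025, then 0.05). Any measure chosen should appear among the listed dependent variables; triglycerides, for example, currently do not.

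The cost is a change of wording, with no extra patients or visits and no loss of primary power. The downside is that some secondary results could no longer be called significant, and without the optional step the two comparative secondary objectives would be answered by estimates instead of formal claims.
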